13.5. RD Event Rate Monitoring

A monitoring tracking system of the RD event rate will be used during the study. The RD event rate will be evaluated on a regular basis and one of the following possible outcomes may result:

- Continue the study with a total of 1,650 subjects if the RD event rate falls within the Interval Confidence (IC at 95%).
- If the RD event rate is greater than IC up, the study could early terminate.
- If the RD event rate is lower than IC low but greater than or equal to 6% , all data collected will be used for derivation of the risk score.
- If the RD event rate is lower than 6%, the sample size will be re-estimated

If the sample size must be increased, Medtronic will determine whether or not to continue the study.

PRODIGY CIP

14. Ethics

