13.1. Sample Size

The size of the study cohort has been calculated to provide independent samples for derivation and validation cohort. At the study closure, subjects will be randomly assigned (2:1) into two groups to create a derivation cohort with 2/3 of the subjects and an internal validation cohort with the other 1/3 allowing to the following calculation.

According to a generally accepted rule of thumb, at least 10 events per variable are expected to be entered into the logistic regression model²⁰. The three following endpoints from RD definition have been taken into consideration to calculate the sample size (since we assumed that the variations in respect to enrollment values could be mostly included into these):

- A. RR \leq 8 bpm for \geq 3 minutes
- B. $SpO_2 \le 85\%$ for ≥ 3 minutes
- C. etCO₂ \geq 60 mmHg for \geq 3 minutes

From literature the incidence of the above events is at minimum:

 $A = 1.4\%^{21}$.

 $B = 10\%^8$ (extrapolation from Figure 3 of Sun et al.).

C = 1% (since we could not find literature data we arbitrarily suppose a low incidence).

The probability that at least one event among A or B or C occur is the probability (P) of the union (U) of A and B and C minus the probability of their intersection (\cap) as follow:

 $P(A \cup B \cup C) = P(A) + P(B) + P(C) - P(A \cap B) - P(A \cap C) - P(B \cap C) - P(A \cap B \cap C) = 12\%.$

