13.1.1. Derivation Cohort Sample Size

The size of the derivation cohort has been calculated to provide at least 10 events per variable that we expect to enter into the logistic regression model. Recording at least 120 RD events would allow around 12 predictor variables to be entered into logistic regression. Assuming an incidence of 12% of subjects with RD episodes and 12-variables for prediction rule, a sample size of 1000 subjects is needed for the derivation cohort.

The selection of 12 high risk variables for the prediction rule has been based on literature review^{1,4,7,16,17,22}:

- Age > 65 y.
- Known or suspected sleep-disordered breathing (OSA, snoring, etc.).
- High risk surgery \leq 24 hours.
- PCA or epidural or intrathecal therapy.
- Obese (BMI >30).
- Multiple opioid or concurrent CNS/sedating medication (benzodiazepines, sleep aids, muscle relaxant, etc.).
- High opioid dosage (>30mg oral morphine per day or equivalent).
- Major organ failure.
- Diabetes.
- Chronic heart failure or other significant cardiac disease.
- Smoke (> 20 packs per year).

Version 3.0, 29 Nov 2016

PRODIGY CIP

- COPD or other significant pulmonary disease (including respiratory events before ward admittance).

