13.3. Primary Endpoint

At the end of data collection all subjects enrolled will be randomly assigned to the derivation set and the validation set at a ratio of 2 to 1. According to the outcome of the planned RD event rate monitoring, there could be the possibility to use the overall population as the derivation cohort. The validation sets will be performed using a bootstrapping method. A detailed description of the bootstrap method will be

Version 3.0, 29 Nov 2016

PRODIGY CIP

reported in the Statistical Analysis Plan (SAP). Bivariate odds ratios (ORs) and 95% confidence intervals (95% CIs) will be estimated. The possibility of collinearity between categorical variables will be also tested. The logistic regression model will be performed using a backward stepwise selection procedure in which the presence of event will be the dependent variable. Independent predictors will be entered into the model if a significant association, defined as $p \le 0.05$, will be identified from bivariate analysis and, to avoid over-fitted and unstable model the correlation coefficient between them should be less than 0.25.

The predictive risk score for RD will be calculated by multiplying each b coefficient (from the multivariate model by 10 and rounding to the nearest integer. The integers will then be added together to produce an overall RD risk score for each subject. The resulting continuous distribution of total risk scores across all subjects in the derivation set will be then stratified into 3 categories of points that grouped subjects according to the level of risk (low, medium and high risks). Model prediction performance will be assessed using calibration (the agreement between predicted and observed outcome) and discrimination (the ability to separate subjects with and without the outcome) and the R2 will be reported as an overall measure for discrimination and calibration. The Sensitivity and Specificity and the receiver-operating characteristic (ROC) curves will be used to visualize the overall accuracy of the model. The discriminatory performance of the model will be validated by comparing the ROC curve analysis in the derivation set with that in the validation set.

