7.6 Derived variables

The statistical evaluations will use some derived variables as listed below. All additional derived variables or changes on the variable listed below are reported in the Statistical Programming Requirements document.

New Variables	Derivation
Monitoring Exposure (minutes)	End monitoring date/time – Start monitoring date/time
Study Exposure (days)	(Study Exit date – date of enrollment)/30.44
BMI35	If BMI >35 then BMI35=1 otherwise BMI35=0
Obese	If BMI >30 then Obese=1 otherwise Obese=0
AGE50	If Age >50 then AGE50=1 otherwise AGE50=0
AGE65	If Age >65 then AGE65=1 otherwise AGE65=0
STOP BANG SCORE	The score is the sum of the following points for each patient: If Snoring loudly= Yes then add 1 point If Tiredness in daytime= Yes then add 1 point If Observed apnea during sleep= Yes then add 1 point If Treated for High blood Pressure= Yes then add 1 point If Body mass index >35 (kg/m2) then add 1 point If Age >50 years then add 1 point If Neck circumference >40 cm (16 inches/17inches according to gender) then add If Gender = Male then add 1 point
Opioids Tolerant §	The FDA definition will be used: A patient is considered opioid tolerant if for at least 1 week he/she has been receiving one of the following: 
 • 60 mg oral morphine/day • 25 mcg transdermal fentanyl/hour • 30 mg oral oxycodone/day • 60 mg oral hydrocodone/day • 8 mg oral hydromorphone/day • 25 mg oral oxymorphone/day • Equi-analgesic dose of any other opioid The Morphine Milligrams Equivalent will be used.
STOP BANG SCORE Class	If 0≤STOP-BANG score ≤2 then STOP BANG SCORE Class= 1 labeled as “Low risk of OSA” If 3≤STOP-BANG score ≤4 then STOP BANG SCORE Class= 2 labeled as “Intermediate risk of OSA” If 5≤STOP-BANG score ≤8 then STOP BANG SCORE Class= 3 labeled as “High risk of OSA”
High Risk Surgery	If occurred within 24 hours
Known or suspected sleep-disordered breathing§	if “Yes to OSA (from Medical History) + YES to first 4 questions of the Apnea History
PCA or epidural or intrathecal therapy	PCA with route as epidural or intrathecal from CM
Multiple opioid or concurrent CNS/sedating medication	According to the Medication coding *(benzodiazepines, sleep aids, muscle relaxant, etc.)
Opioid dosage	According to the Medication coding * (>30mg oral morphine per day or equivalent)
Major organ failure	According to the coding °
Diabetes	if “Yes to Diabetes type I or II”

New Variables§	Derivation

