7.10.1.1 Deriving the model

Note for Programmer: The analysis for the primary objective will be performed on a Dataset with one row per patient with RD episode as validated by CEC as the dependent variable (at least one RD) and baseline predictors as independent variables. Potential predictors will be reported on continuous scale or grouped into categories.

The logistic model will be used for bivariate e multivariate odds ratios (ORs) and 95% confidence intervals (95% CIs) will be estimated for each potential predictor. The following steps will be followed to derive the score for each predictor according to categories⁴:

- Determine categories for each risk factors (the most will be 0/1)
- Determine reference class for each risk factor (for dummy the reference category is 0)
- Calculate mid-values to represent categories
- Determine multiplier β
- Determine point score for each risk factor category

If **Data Split** approach:

- Repeat multivariate model on the validation set
- Calculate performance measures
- The "Optimism" is the difference between the performance measures from validation and derivation set

If **Bootstrapping** approach:

- 500 bootstrapped replications of the multivariate model

- Calculate performance measures bootstrapped
- The difference between the bootstrapped performance and the model performance will be averaged to obtain an estimation of the “optimism” of the model. The optimism will be used to validate the model.

Table 25 - RD Risk Score Derivation identified by logistic – MFAS

Predictors	Bivariate analysis OR (95% CI) (N=XXXX)	Multivariate analysis OR (95% CI) (N=XXXX)	Coefficient	Adjusted Coefficient	Risk score point
Char#1	x.xx (x.xx- x.xx)	x.xx (x.xx- x.xx)	x.xxx	x.xx (x.xx- x.xx)	xx
Char#2	x.xx (x.xx- x.xx)	x.xx (x.xx- x.xx)	x.xxx	x.xx (x.xx- x.xx)	xx
...					
Char#N	x.xx (x.xx- x.xx)	x.xx (x.xx- x.xx)	x.xxx	x.xx (x.xx- x.xx)	xx

The collinearity between categorical variables will be also tested by means the Cramer V test for nominal variables and Kendal’s tau-b for ordinal variables. The multivariate logistic regression model will be performed using a stepwise selection procedure in which the presence of event will be the dependent variable. Independent predictors will be entered in to the model if a significant association, defined as $p \leq 0.05$, will be identified from bivariate analysis and, to avoid over-fitted and unstable model the correlation coefficient between them should be less than 0.25.

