9.2 Bootstrap Method

Bootstrapping will be considered as an alternative method of internal validation that involves taking a large number of samples with replacement from the original sample. Bootstrapping provides unbiased estimates of predictive accuracy and it has the advantage to use the entire dataset for model development. A total of 500 bootstrapped replications will be performed. For each replication the univariate and multivariate models will be run. According to results, the R^2 as the average of R^2 from each replication will be calculated. The difference between average bootstrapped R^2 and model R^2 will represent the "optimism" of the model compared to the bootstrapped models. The optimism will consider as the validation of the model.

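### Protocol 13.5 lets the risk score be derived on pooled data down to a 6% RD rate, where about 89 to 99 events support 8 or 9 variables, not the 120 events and 12 variables the study was sized on; the 12% sizing rate also uses a different RR criterion from the endpoint

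*Protocol*

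**What the plan says.** **Sizing.** Protocol 13.1 adopts the rule of thumb that "at least 10 events per variable are expected to be entered into the logistic regression model". Section 13.1.1 applies it: "Recording at least 120 RD events would allow around 12 predictor variables to be entered into logistic regression". At an assumed 12% RD rate this gives 1000 subjects for derivation. A further 500 for validation and a 10% allowance for losses bring enrolment to 1650. SAP 6 repeats this.

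**Rate monitoring.** Protocol 13.5 has four branches. In the third, when the RD rate is "lower than IC low but greater than or equal to 6% , all data collected will be used for derivation of the risk score". Re-estimation is reserved for rates below 6%. The limits of the interval are not given as numbers, and no reason is given for 6%. Protocol 13.3 refers to the same route: "there could be the possibility to use the overall population as the derivation cohort". The SAP does not restate the 6% figure.

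**Choice of variables.** In SAP 7.10.1.1, bivariate odds ratios "will be estimated for each potential predictor". Then "Independent predictors will be entered in to the model if a significant association" is found at p ≤ 0.05, provided the correlation between predictors is below 0.25, and stepwise selection follows. Protocol 13.3 is similar. SAP 7.2 and 7.10.1 mention events per variable, without a threshold, only as a ground for choosing between the 2:1 split and the bootstrap. SAP 7.12 promises a new strategy if the event rate falls and points to the bootstrap section.

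**The 12%.** Protocol 13.1 and SAP 6 build it from three components, each lasting at least 3 minutes: RR ≤8 (1.4%), SpO₂ ≤85% (10%) and etCO₂ ≥60 mmHg (1%). They present these as taken from the RD definition. That definition (Protocol 5.2.1, SAP 7.10.1) has RR ≤5, and it adds etCO₂ ≤15 mmHg, apnea longer than 30 seconds and any rORADE.

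**The concern.** The score is the primary deliverable, and 13.5 is the control meant to ensure enough events to derive it. A lower bound for proceeding without re-estimation should either deliver the event count used for sizing or say what reduced model it supports. The 6% bound does neither. If the rate fell between 6% and about 8%, the score would be derived on fewer than 120 events, and the number of variables in the model would depend on p-values and correlations rather than on the events available.

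The RR mismatch bears on the same control. The 12% fixes the sample size and is presumably the reference for the 13.5 interval, yet it was not built from the endpoint as defined.

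**Working it through.** **1. Reproduce the plan.** Events: 10 × 12 = 120. Derivation cohort: 120 / 0.12 = 1000. Both cohorts: 1000 × 3/2 = 1500. Enrolled: 1500 × 1.10 = 1650. These match Protocol 13.1.1 and 13.1.2.

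**2. Analysed number.** The documents do not fix how many subjects pooling would analyse, so three values are used: 1485 (1650 less 10%), 1500 (the planned cohorts) and 1650 (all enrolled).

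**3. Pooled events.** Events = rate × n. Variables supported = events / 10, rounded down. Rate needed for 120 events = 120 / n.

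| Analysed n | Events at 6% | Below 120 by | Events per variable if 12 enter | Variables at 10 each | Events at 7% | Rate for 120 events |
|---|---|---|---|---|---|---|
| 1485 | 89.1 | 25.8% | 7.4 | 8 | 104.0 | 8.1% |
| 1500 | 90 | 25.0% | 7.5 | 9 | 105 | 8.0% |
| 1650 | 99 | 17.5% | 8.3 | 9 | 115.5 | 7.3% |

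For 120 events at 6%, 120 / 0.06 = 2000 analysed subjects are needed, 350 more than will be enrolled. Chance would rarely make up the difference: with a true rate of 6%, the binomial probability of 120 or more events is about 0.1% at 1485 or 1500 and 1.9% at 1650.

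**4. Where the shortfall lies in the pooling band.** Assume a normal-approximation interval centred on 12%. Its lower limit is 0.12 − 1.96 × √(0.12 × 0.88 / n), which is 9.2% at n = 500, 10.0% at 1000 and 10.4% at 1500 or 1650. On that assumption pooling does meet the 120-event basis from about 8% up to the lower limit. The shortfall runs from 6% to about 8%. The counts at 6% do not depend on this assumption.

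**5. The 12% and the RR criterion.** Under independence, 1 − 0.986 × 0.90 × 0.99 = 12.1%, which reproduces the plan's 12%. RR ≤5 is a subset of RR ≤8, so its incidence lies between 0 and 1.4%. With the RR term at zero, 1 − 0.90 × 0.99 = 10.9%. Replacing RR ≤8 by RR ≤5 therefore puts the three-component rate between 10.9% and 12.1%, or about 109 to 121 events per 1000. The omitted components (apnea, low etCO₂, rORADE) can only add to that, by an amount the documents do not give.

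**The case against.** **The rule counts variables entered, and 12 is approximate.** This stands. With 90 events, up to 9 entered variables satisfy 10 per variable, and screening and stepwise selection may leave that many or fewer. A reader might infer that the plan breaks its own rule at 6%, or that the score will be overfitted by a known amount. The documents support neither. In the pooled branch the SAP would also estimate optimism: "For each replication the univariate and multivariate models will be run" (SAP 9.2). But the bootstrap measures optimism after fitting. It neither supplies events nor sets the number of variables.

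**120 is a target, not a floor.** This also stands. On the interval assumed above, the branch that continues unchanged could accept 10.4%, which gives 104 events in a derivation cohort of 1000, about what pooling 1500 gives at 7%. Pooling is itself a help: at 6% it raises 60 events (1000 subjects) to 90 (1500). None of this explains 6%, where the count is lower still.

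**Events per variable is already considered.** It is, in SAP 7.2 and 7.10.1, but only for the validation method and without a number.

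**Low rates may be unlikely.** The component incidences are described as minima, and parts of the endpoint were left out. That bears on how often the branch would be used, not on what it delivers.

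Three further inferences should be resisted. Adding other derived variables in SAP 7.6, such as the age and BMI cut-offs used in STOP-BANG, to the candidate count would worsen the ratio, but no passage names them as candidates. The early stop for a high rate in Protocol 13.5 and 15.8 lacks an event count, but it is permissive and contradicts nothing. And the RR mismatch does not show that 12% is too high, because the omitted components act in the other direction.

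**Conclusion.** Two statements are wrong as written. First, the 6% threshold does not deliver the stated basis of 120 events and around 12 variables. It delivers about 89 to 99 events, 17.5% to 25.8% short, enough for 8 or 9 entered variables. The stated basis is reached only from about 7.3% to 8.1%. This rests on an assumed 1485 to 1650 analysed subjects and holds across that range. No passage ties the number of variables entered to the events available. How much overfitting would follow cannot be stated from the documents.

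Second, the 12% is not derived from the endpoint as defined, because the sizing text uses RR ≤8 and the endpoint RR ≤5. The RR change alone lowers the three-component rate by at most 12.1% − 10.9% = 1.2 percentage points under independence. The net direction is unknown.

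Both should be corrected. Neither calls for a change of design.

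**What to change.** 1. **Protocol 13.5.** Beside the 6% threshold, state that at 6% the pooled data (about 1500 subjects, 90 with RD) support about 9 model variables at 10 events per variable, not 12, and that 120 events need a rate of about 8%.
2. **SAP 7.10.1.1.** State that the number of parameters entered in the multivariate model, including any centre or country terms, will not exceed the number of subjects with CEC-confirmed RD in the derivation data divided by 10, with the order of priority fixed before outcome data are seen.
3. **Protocol 13.1 and SAP 6.** Reconcile the RR criterion with the endpoint definition, and state that the 12% rests on RR ≤8 and on three components only.

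**Cost.** Wording only, with no extra subjects, although the Protocol changes go through the amendment process in 15.5. Fewer predictors may enter at low event rates. The limit also binds in the 2:1 split whenever derivation holds fewer than 120 events: 104 events would allow 10 parameters. If centre were entered as separate indicators for 16 centres, it would take 15 parameters, more than the 12 allowed even at 120 events. The team would then need to say how the centre or country effect is examined within the limit.

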14.1. Statement(s) of Compliance

This clinical study will be conducted in compliance with the Declaration of Helsinki (2013), laws and regulations of the countries in which the clinical study is conducted, including data protection laws, the Clinical Investigation Agreement and the Clinical Investigation Plan.

All principles of the Declaration of Helsinki have been implemented in this clinical study by means of the informed consent process, EC/IRB approval and clinical study training.

If the regulatory authority imposes any additional requirements (e.g. safety reports, progress reports etc.), Medtronic will prepare the required documents and send them to the respective authority.

14.1.1. Ethics Committee / Institutional Review Board

Prior to enrolling subjects in this clinical study, each investigation site's EC/IRB will be required to approve the current Clinical Investigation Plan, the Patient Information and Informed Consent form, including any other written information to be provided to the subjects and, if applicable, materials used to recruit subjects. EC/IRB approval of the clinical study must be received in the form of a letter and provided to Medtronic before commencement of the clinical study at an investigation site. The approval letter must contain enough information to identify the version or date of the documents approved. If this information is not contained in the approval letter, it must be retrievable from the corresponding submission letter. In addition, the approval letter needs to be accompanied by an EC/IRB roster or letter of compliance, to allow verification that the investigator, other investigation site personnel, and/or Medtronic personnel are not members of the EC/IRB. If they are members of the EC/IRB, written documentation is required stating that he/she did not participate in the approval process. If the EC/IRB imposes any additional requirements (e.g. safety reports, progress reports etc.), Medtronic will prepare the required documents and send them to the investigator for reporting to the EC/IRB.

Investigators must inform Medtronic of any change in status of EC/IRB approval once the investigation site has started enrollment. If any action is taken by an EC/IRB with respect to the investigation, that information will be forwarded to Medtronic by the respective investigator.

14.1.2. Regulatory Requirements / Competent Authorities

The study shall be conducted in accordance with the laws and regulations of the countries in which the clinical study is conducted, including data protection laws. In countries where submission to the regulatory authority is required per local law, no subjects will be enrolled in the clinical study until the particular regulatory authority has approved the current Clinical Investigation Plan of the clinical study and other documents as required according to the local requirements. If the regulatory authority imposes any additional requirements (e.g. safety reports, progress reports etc.), Medtronic will prepare the required documents and send them to the respective authority.

14.1.3. Clinical Trial Insurance

The Patient Monitoring & Recovery business unit is an indirect wholly owned subsidiary of Medtronic plc, which as the parent company of such entity maintains appropriate clinical study liability insurance coverage as required under applicable laws and regulations and will comply with applicable law and

Version 3.0, 29 Nov 2016

PRODIGY CIP

custom concerning specific insurance coverage. If required, a Clinical Trial Insurance statement/certificate will be provided to the EC/IRB.

14.1.4. Subject Compensation and Indemnification

While a fee will be provided to the participating centers for each enrolled patient, no additional fee/reimbursement will be provided to the patients.

This trial is conducted in multiple countries, therefore reimbursement and indemnification will be addressed on a country specific basis in the study documents and site Clinical Trial Agreements.

Subjects are treated according to general clinical practice, so no extra tests or follow-ups are required and therefore no risks other than the risks typically associated with a routine device use are anticipated. If injuries happen, it will be treated in the same manner as per routine clinical practice. Costs of these treatments will be covered by the national health insurance (as applicable per country) as in usual clinical practice. The subject pays his/her co-payment for that treatment. No special compensation will be paid by the Sponsor.

15. Study Administration

